6.1 Analysis Plan

Statistical Analysis: The overall analysis will follow Intention-to-treat approach and will use Generalized Linear Mixed Models (e.g. those available in IBM SPSS) including fixed factors following the factorial designs presented in study figure for the specific aims listed below, and random effects reflecting patients' attrition rate.

Metrics:

- (i) Five HbA1c determinations approximately 10 weeks apart;
- (ii) Eight-week sequences of CGM data accompanied by BG self-monitoring readings and recording of the timing of events such as meals and exercise through the GUI
- (iii) Psychometric questionnaires administered concurrently with HbA1c, and
- (iv) Individual structured interview and qualitative/quantitative technology acceptance assessments. CGM data will be used to compute established metrics of risk for hypoglycemia, e.g. the Low BG Index (LBGI), glucose variability, and BG dynamics, as presented in our review of statistical tools for CGM data analysis.

Primary Hypothesis by Specific Aims of the Study

Specific Aim 1: Overnight CLC achieved by USS+SAP(d) will be superior to SAP alone in terms of: (1) Improved HbA1c without increasing the risk for hypoglycemia; (2) Reduced incidence and risk for hypoglycemia overnight, and (3) Reduced fear of hypoglycemia and improved diabetes quality of life scores.

Specific Aim 2: CLC during the day achieved by USS+CLC(d) will preserve the benefits of USS+SAP(d) and will be superior to USS+SAP(d) in terms of: (1) Increased time within target range of 70-180mg/dl during the day; (2) Reduced risk for hypoglycemia during and after exercise, and (3) Reduced postprandial glucose variability.

Specific Aim 3: CLC system acceptance evaluated by an individual structured and technology acceptance scores will be: (1) Superior, for USS+SAP(d) compared to SAP alone, i.e. adding USS overnight will increase patients' acceptance of CLC, and (2) Marginally inferior, for USS+CLC(d) compared to USS+SAP(d); i.e. some patients would prefer SAP alone during the day due to perceived increased system complexity.

Primary Outcomes

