Specific Aim 1: The **primary outcome** is improvement in diabetes control on USS+SAP(d) vs. SAP alone as defined by reduced risk for hypoglycemia (Time <70 mg/dL by CGM) without increase in HbA1c. Repeated Measures ANOVA with covariate will assess this effect. Inversely, comparing HbA1c with covariate overnight Time <70 mg/dL by CGM will address SA1-2, while comparing the psychometric questionnaire scores pre-post treatment will address SA1-3.

Specific Aim 2: The **primary outcome** is improved time within the target range of 70-180mg/dl during the day on USS+ CLC(d) vs. USS+SAP(d). Repeated Measures ANOVA following the study design outlined will assess this effect. SA2-2 will be addressed

comparing frequency of hypoglycemia within the post-exercise periods recorded by the system; SA2-3 will be addressed using Variability-Grid Analysis, and SA-4 will be addressed by a sub-analysis limited to those who did not achieve HBA1c≤7.5% during the first 3 months of the study.

Specific Aim 3: will be addressed by comparing structured interviews and technology acceptance scores along the two sequences of treatment modalities specified in the study design: treatment escalation for Group A and de-escalation for Group B. Analyzing the random effect of patient attrition will shed additional light on system acceptance.

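### SA1 item (1) and the declared SA1 primary outcome swap the roles of HbA1c and hypoglycemia, the no-increase condition on HbA1c has no decision criterion, and the SA1-1 and SA1-2 analyses appear crossed

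*Combined protocol and SAP*

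**What the plan says.** **Hypothesis.** SA1 compares USS+SAP(d) with SAP alone. Its first item, in Section 1.1 and again in Section 6.1 under the primary hypotheses, is "1) Improved HbA1c without increasing the risk for hypoglycemia". Its second item is "2) Reduced incidence and risk for hypoglycemia overnight".

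**Primary outcome.** Section 6.1, Primary Outcomes, defines the SA1 primary outcome as improved diabetes control, meaning "reduced risk for hypoglycemia (Time <70 mg/dL by CGM) without increase in HbA1c". The analysis is one sentence: "Repeated Measures ANOVA with covariate will assess this effect". The covariate is not named.

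**SA1-2.** The next sentence reads "Inversely, comparing HbA1c with covariate overnight Time <70 mg/dL by CGM will address SA1-2".

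**SA2, for contrast.** The SA2 primary outcome states its time window: "improved time within the target range of 70-180mg/dl during the day". SA2-2, which concerns exercise hypoglycemia, is given a hypoglycemia outcome: "comparing frequency of hypoglycemia within the post-exercise periods recorded by the system".

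**Data.** Section 6.1 plans "Five HbA1c determinations approximately 10 weeks apart" and eight-week CGM sequences. HbA1c is measured at baseline (Section 2.3.2) and after each phase (Sections 3.7 and 3.8).

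**The concern.** The hypothesis makes HbA1c the superiority target and hypoglycemia the constraint. The primary outcome does the opposite. A trial that lowers HbA1c and leaves Time <70 unchanged satisfies item (1) and fails the primary outcome. A trial that lowers Time <70 and leaves HbA1c unchanged meets the primary outcome and fails item (1).

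The second half of the primary outcome cannot be judged as written. A model with Time <70 as the dependent variable does not show whether HbA1c rose, whatever the covariate is. With no stated criterion, the likely default is to accept a non-significant HbA1c difference as no increase, which can let a real rise through.

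Taken literally, SA1-2 would be answered with an HbA1c result. Overnight hypoglycemia would enter only as a covariate, and one measured after treatment began.

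**Working it through.** **1. The SA1 statements side by side**

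| Place | Superiority on | Must not worsen | Analysis |
|---|---|---|---|
| SA1 item (1), Sections 1.1 and 6.1 | HbA1c | Hypoglycemia | None listed under this label |
| SA1 primary outcome, Section 6.1 | CGM Time <70 | HbA1c | ANOVA with unnamed covariate |
| SA1 item (2), Sections 1.1 and 6.1 | Overnight hypoglycemia | None | HbA1c compared, overnight Time <70 as covariate |

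The HbA1c comparison fits item (1) and the Time <70 comparison fits item (2), so the two look crossed. The primary Time <70 carries no time window. Unless it is meant to be overnight, no listed SA1 analysis has overnight hypoglycemia as its dependent variable.

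**2. The plan's own sample size**

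Section 6.2 gives f = 0.2, alpha 0.01, power 90%, correlation 0.4, attrition up to 31%, 76 completers and 110 randomized. For a repeated-measures F test with k = 2 groups and m = 4 measures (m is inferred from the four phases):

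- λ = f²·N·m/(1−ρ) = 0.04 × 76 × 4/0.6 = 20.3, with df 3 and (76−2) × 3 = 222.
- Power is 0.909. The minimum N is 75, or 76 with equal groups. 76/0.69 = 110.1.

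The stated figures reproduce. They cover a single F test, not a joint criterion on two endpoints.

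**3. What a rule of no significant increase would let through**

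From the plan: n = 76 completers. Assumed: one paired comparison, paired-difference SD of 0.4, 0.5, 0.6 or 0.8 HbA1c points, and a two-sided alpha of 0.01 or 0.05 for HbA1c.

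- Largest observed rise that passes: t(1−α/2, 75) × SD/√76. At 0.01 and SD 0.4 this is 2.643 × 0.4/8.718 = 0.121.
- Chance that a true rise δ passes: the noncentral t distribution with 75 df and noncentrality δ√76/SD, evaluated at the critical value.

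| Paired SD | Bound, 0.01 | True rise 0.1 passes, 0.01 | True rise 0.2 passes, 0.01 | Bound, 0.05 | True rise 0.1 passes, 0.05 | True rise 0.2 passes, 0.05 |
|---|---|---|---|---|---|---|
| 0.4 | 0.121 | 67% | 5% | 0.091 | 42% | 1% |
| 0.5 | 0.152 | 81% | 20% | 0.114 | 59% | 7% |
| 0.6 | 0.182 | 88% | 40% | 0.137 | 70% | 18% |
| 0.8 | 0.243 | 93% | 67% | 0.183 | 81% | 42% |

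Each sequence has two USS+SAP(d) periods. With equal variances and correlations, averaging them changes the contrast variance from 2σ²(1−ρ) to 1.5σ²(1−ρ), so the SD shrinks by √0.75 = 0.866. At 0.01 and paired SD 0.4 to 0.6, a true 0.1 rise then passes 55% to 83% of the time and a 0.2 rise 1% to 24%.

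**4. Power of a proper HbA1c test**

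Assumed: true difference zero, n = 76, one-sided 0.005, one paired comparison, illustrative margins of 0.2 and 0.3 points. Power is the chance that a noncentral t with 75 df and noncentrality margin × √76/SD exceeds 2.643.

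| Paired SD | Margin 0.2 | Margin 0.3 |
|---|---|---|
| 0.4 | 95% | over 99% |
| 0.5 | 80% | 99% |
| 0.6 | 60% | 95% |
| 0.8 | 33% | 73% |
| 1.1 | 15% | 40% |

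The last row comes from the plan's correlation of 0.4 with an assumed HbA1c SD of 1.0: 1.0 × √(2 × 0.6) = 1.10. If Time <70 has its planned 90% power and the two tests are independent, joint power at the 0.2 margin runs from 0.90 × 0.954 = 0.86 (SD 0.4) to 0.90 × 0.154 = 0.14 (SD 1.1).

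**The case against.** **The plan does compare HbA1c, and it does name a primary outcome.** Both are true. A reader might infer that HbA1c is never tested or that SA1 has no defined primary. Section 6.1 supports neither: it lists a treatment comparison of HbA1c, and it identifies reduced Time <70 without an HbA1c increase as primary. What is missing is a criterion for no increase and agreement with item (1).

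**The covariate may be baseline HbA1c.** A reader might infer that the primary analysis adjusts for on-treatment HbA1c, and so conditions on something treatment affects. The word that opens the SA1-2 sentence points that way, but the covariate is unnamed and a baseline HbA1c exists. That criticism is therefore conditional. The HbA1c comparison assigned to SA1-2 is different: its covariate, overnight Time <70 by CGM, is named and most naturally read as the treatment-period value.

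**SA1 has three items.** A fall in Time <70 with unchanged HbA1c fails item (1) but would support item (2) if the fall is overnight. This softens the conflict without removing it.

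**SA1-2 may be a labelling slip.** Probably so. Swapping the labels would repair most of that part, but the time window would still need stating. The general mixed-model text in Section 6.1 names no SA1-2 test.

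**The figures rest on assumptions.** They do, and nothing in the documents makes a 0.1-point rise clinically important. They illustrate why a rule is needed and do not predict this trial.

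**Sample size.** A reader might conclude that N is wrong. It reproduces. Section 6.2 does not name the endpoint behind f = 0.2, but that is a minor side point and not part of this finding.

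**Conclusion.** The point holds and should be fixed. Three things follow from the text alone. SA1 item (1) and the declared SA1 primary outcome assign opposite roles to HbA1c and hypoglycemia. The no-increase condition has no non-inferiority criterion or decision rule. SA1-2 is assigned an HbA1c comparison although its hypothesis is about overnight hypoglycemia.

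The size is illustrative because the documents give no HbA1c SD, margin or alpha for this condition. At two-sided 0.01 and paired SD 0.4 to 0.6, a true 0.1-point rise would pass a non-significance rule 67% to 88% of the time with one paired comparison, or 55% to 83% if the two USS+SAP(d) periods are averaged.

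**What to change.** (a) For SA1-2, make overnight CGM Time <70 the dependent variable.

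(b) Align SA1 item (1) in Sections 1.1 and 6.1 with the declared primary outcome. The sponsor chooses which text moves. State the time window of the primary Time <70 and name the covariate.

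(c) Judge the no-increase part, for whichever endpoint it ends up covering, in a separate treatment comparison. That endpoint is the dependent variable, with no post-treatment covariate; baseline adjustment is acceptable. The criterion is an upper confidence bound below a margin, with margin and alpha fixed by the sponsor before analysis. State that SA1 success requires both parts. Versions adjusted for the other endpoint are supportive only.

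**Cost.** Text changes, one margin and one alpha; the HbA1c and CGM data are already planned. The real cost is power. Requiring both parts lowers the chance of success, and the loss is small or severe depending on an SD the documents do not give. The sponsor should estimate the paired SD from its own data, without looking at treatment differences, before fixing the margin. A less strict alpha eases the loss: at one-sided 0.025 and a 0.2-point margin, HbA1c power is 99% at paired SD 0.4, 82% at 0.6, 58% at 0.8 and 35% at 1.1.

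### The SA1 primary analysis adjusts Time <70 mg/dL for an unnamed, untimed covariate; read naturally it is HbA1c under treatment, which would bias the treatment contrast

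*Combined protocol and SAP*

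**What the plan says.** Section 6.1 (Primary Outcomes, Specific Aim 1) sets the primary outcome as better control on USS+SAP(d) than on SAP, "as defined by reduced risk for hypoglycemia (Time <70 mg/dL by CGM) without increase in HbA1c". The primary analysis, and then the analysis for SA1-2, are given in two consecutive sentences: "Repeated Measures ANOVA with covariate will assess this effect. Inversely, comparing HbA1c with covariate overnight Time <70 mg/dL by CGM will address SA1-2". In the first of these, no covariate is named, and no time point is given for it.

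The hypotheses earlier in 6.1 list, as effects of USS+SAP(d), "Improved HbA1c without increasing the risk for hypoglycemia" and "Reduced incidence and risk for hypoglycemia overnight". The metrics are "Five HbA1c determinations approximately 10 weeks apart" and "Eight-week sequences of CGM data accompanied by BG self-monitoring readings". HbA1c is measured at baseline (2.3.2, 3.1) and after each treatment phase (3.7, 3.8).

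No margin, separate test or decision rule is given for the requirement that HbA1c not increase.

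**The concern.** If the covariate is HbA1c measured under treatment, the primary model conditions one result of treatment on another. The question then changes from whether Time <70 fell to whether it would have fallen had HbA1c stayed the same. That is not the outcome defined in 6.1.

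The direction matters. SA1 predicts that HbA1c falls on USS+SAP(d). If, within a subject, lower HbA1c goes with more time below 70, the model credits the expected extra hypoglycemia back to the device, and a null effect can be reported as a benefit. If HbA1c rises, the bias reverses and a real reduction can be hidden. In neither case does the adjustment show that HbA1c did not increase, because adjusting for a variable does not test it.

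**Working it through.** **1. The plan's own figure.** Section 6.2 gives f = 0.2, alpha 0.01, power 90%, correlation 0.4, 76 completers and 110 randomized. For a within-subject factor with m = 4 levels, lambda = f² × m × N / (1 − rho) = 0.04 × 4 × 76 / 0.6 = 20.27. Power at N = 76 is 0.91, and 90% is first reached at N = 75. Attrition: 76 / 0.69 = 110.1. The stated numbers reproduce. The calculation has no covariate term; the present point concerns bias and changes no stated N.

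**2. Which covariate?**
- Variable: the second analysis has HbA1c as outcome and Time <70 as covariate. Its inverse is Time <70 as outcome and HbA1c as covariate.
- Timing, primary analysis: the condition on HbA1c concerns its value under treatment, and a value exists after every phase.
- Timing, mirror analysis: the listed CGM metric is the eight-week phase record. Section 3.3 exempts recent Dexcom users from the CGM run-in, so no CGM baseline is common to all subjects.

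**3. Bias formula.** Let D be a subject's difference in Time <70 (USS+SAP(d) minus SAP) and H the same difference in HbA1c. Fit D = a + bH + error and read a as the adjusted effect. Then a = mean(D) − b × mean(H), with b = r × SD(D) / SD(H).

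**4. Inputs.** From 6.2: 76 pairs and alpha 0.01. Assumed, because the documents do not give them: SD(H) = 0.4%, SD(D) = 1.5 points, r from −0.2 to −0.5, mean(H) from 0 to −0.3%. The change-on-change regression is also an assumed form of the model.

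Slopes: r = −0.2 gives −0.2 × 1.5 / 0.4 = −0.75 points per 1% HbA1c; r = −0.3 gives −1.125; r = −0.5 gives −1.875.

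**5. True effect on Time <70 of zero** (20,000 simulated trials per cell; repeat runs agree within 2 percentage points):

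| HbA1c fall | r | Adjusted effect (points) | False-positive rate |
|---|---|---|---|
| 0.2% | −0.2 | −0.15 | 3.4% |
| 0.2% | −0.3 | −0.22 | 8.5% |
| 0.2% | −0.5 | −0.37 | 34% |
| 0.3% | −0.2 | −0.23 | 6.7% |
| 0.3% | −0.3 | −0.34 | 16% |
| 0.3% | −0.5 | −0.56 | 65% |
| 0 | any of these | 0 | 1% |

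Hand check of the 65% row: residual SD = 1.5 × √(1 − 0.25) = 1.30; SE(a) = 1.30 × √(1/76) × √(1 + (0.3/0.4)²) = 0.186; 0.5625 / 0.186 = 3.02 against a critical value of 2.64, which gives a rejection rate of about 65%. The analysis without the covariate rejects in about 1% of trials throughout.

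**6. True increase of 0.25 points, HbA1c fall of 0.3%.** The adjusted effect is 0.25 − 0.225 = +0.03 (r = −0.2), 0.25 − 0.3375 = −0.09 (r = −0.3) and 0.25 − 0.5625 = −0.31 (r = −0.5).

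**7. Baseline covariate.** HbA1c before randomisation cannot be changed by treatment, so once mean-centred it leaves the expected within-subject contrast unchanged. In a check where baseline strongly predicted the change (correlation −0.5), the null rejection rate was 2.4%. The excess over 1% comes from a slightly small standard error, not from bias.

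**The case against.** The strongest reply is that the plan never states the fault. A reader might infer that 6.1 prescribes adjustment for on-treatment HbA1c; it does not. It says only that there is a covariate. Baseline HbA1c is collected, section 2.1 aims to match the groups on it, and a classical repeated-measures ANOVA takes one covariate value per subject, which fits a baseline value. On the other hand, the mixed models named at the start of 6.1 can take a value for each phase. Both readings are open, and on the baseline reading the bias disappears. This part of the reply stands.

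A reader might also infer that the mirror covariate has to be on-treatment. That is likely but not forced: section 3.3 uses the run-in of CGM non-users to help establish baseline control, and allows download of data from CGMs already in use. Coverage would be incomplete, and this is not the primary analysis.

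A third tempting inference is that real harm would be reported as benefit. Step 6 shows no sign change at r = −0.2. With a 0.2% fall the sign also stays positive at r = −0.2 and −0.3. A true 0.25-point increase is declared a significant reduction in 0.3%, 1.5% and 17.5% of simulated trials for a 0.3% fall (r = −0.2, −0.3, −0.5), and in at most 3.5% for a 0.2% fall.

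Finally, the false-positive range rests wholly on assumed values; with a 0.1% fall it runs from under 2% to about 8%. The pilot difference in section 1.2 (1.56% − 0.55% = 1.01 points) is a weak yardstick: 10 subjects, overnight use, p = 0.06, whereas the primary Time <70 is not limited to the night.

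What the reply does not remove is that the covariate of the primary test is unspecified, that the most natural reading is the biased one, and that no covariate adjustment can establish that HbA1c did not rise.

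**Conclusion.** The point holds with moderate confidence. As most naturally read, section 6.1 adjusts one expected treatment effect for another, and this biases the SA1 primary contrast whenever HbA1c responds to treatment and is associated within subjects with Time <70. SA1 itself predicts the first condition. Under the assumptions in step 4, with a fall of 0.2-0.3%, the spurious reduction is 0.15-0.56 points and the false-positive rate about 3%-65% against a nominal 1%. Without an HbA1c change there is no bias, and with a rise it reverses. These figures illustrate the mechanism and do not predict this trial's result. If a mean-centred baseline HbA1c was intended, the defect in the primary analysis is reduced to an omission: the plan must say so, because otherwise the covariate can be chosen after the data are seen. The condition on HbA1c remains untested under either reading.

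**What to change.** In section 6.1:
- State that HbA1c measured under treatment is not a covariate for Time <70, and that Time <70 measured under treatment is not a covariate for HbA1c.
- Estimate the USS+SAP(d) minus SAP contrast for each outcome without adjustment for the other.
- Allow only covariates that are named and measured before randomisation, for example baseline HbA1c, age and gender, mean-centred.
- Assess the condition on HbA1c from the separate HbA1c contrast and its confidence interval. The documents give no margin, so the sponsor has to set the rule by which that interval is judged, and do so in advance.

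The same edit should give SA1-2, which is a hypothesis about overnight hypoglycemia, an analysis with overnight hypoglycemia as its outcome.

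The cost is wording only: no additional data or subjects, and no change to the stated N.

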1.5.2 Protocol Summary

For the proposed studies, the AP system will be deployed with different functionalities at different stages of the trial, resulting in variation in what the subject will be responsible for and what the system will drive. A trial outline is contained in Figure 1 and visits detailed in Figure 5. **Study Phases without the AP system**

CGM Run-in Phase: Study participants will begin with a maximum 2 week run-in period during which they will have a CGM (i.e. sensor-augmented pump therapy or CGM+CSII) but otherwise be on their usual diabetes management with respect to BG monitoring, pump basal rates, insulin-to-carbohydrate ratios and correction factors. This is necessary because some of the study participants will not have had experience with CGMs in the past.

Study Pump Run-in Phase: All subjects will have a run-in period on the study pump of up to two week duration. Subjects who have had prior experience with the study pump may either skip this run-in phase or may require a shorter run-in period depending on their proficiency with the study pump.

Sensor-Augmented Pump (SAP) Therapy: During this phase, the subject is on the study CGM and their personal insulin pump. There are no predictive or control algorithms. The subjects will administer basal and bolus insulin using their usual home insulin parameters.

Study Phases with the AP System

AP system Run-In Phase: Subjects who have not had recent use of the system (more than approximately 2 weeks of use in the past 6 months or more than 2 months of use in the past year) will complete an up to 2-week home use period with the full system in pump only (open loop) configuration where no closed loop algorithms are activated. Subjects who have had prior experience with the system as defined above will not be required to do Visit 5.

USS+SAP (d): USS Virginia plus SAP during the day (d). Subjects will be using the study pump and CGM with the AP system in Pump mode (open loop only, no closed loop algorithms running). The subject will activate the USS Virginia Closed-Loop Control as early as pre-dinner but is expected to activate CLC by bedtime. The subject will continue in Closed-Loop Control until the time of awakening in the morning. The USS will monitor CGM and insulin-on-board data and predicts the patient's risk of hypoglycemia and adjust insulin delivery accordingly.

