The subject must be able to complete system-related tasks independently to be eligible to continue in the study.

3.6 Visit 5 - AP System Run-In phase: Home Use in Pump Only (Open Loop) Configuration

Eligible subjects who have not had recent use of the system (more than ~2 weeks of use in the past 6 months or more than ~2 months of use in the past year) will complete up to 2-week home use period with the full system in pump only (open loop) configuration where no closed loop algorithms are activated. Subject will be instructed not to start closed loop during this run-in phase. Subjects who have had prior experience with the AP system as defined above will not be required to do Visit 5. Subjects who are demonstrating proficiency, as determined by the study physician, may have a shorter open loop run-in phase with a minimum of 5 days duration Criteria for proficiency is listed in section 3.11.

For the inControl system, remote monitoring will be available during this period for the purposes of data collection and ad hoc assessment of system performance by study team. The study team will be available for the subject to contact during this phase. Study staff will contact the subject and review data on the Remote Monitoring once daily. The subject may contact the study staff at any time.

For the Tandem-G6 system, remote monitoring will not be available. Study staff will contact the subject daily to assess difficulties with the use of the system. The subject may contact the study staff at any time. If the study team requires additional information, the subject may be asked to upload the pump at home so that the study can review data on the t:connect website.

3.7 Visit 6 + Visit 7 + Visit 8 Washout Following Completion of the Each Study Phase

At the completion of the each phase of the study, subjects will have up to a two week washout prior to proceeding to the next phase.

First Phase: Group A 8 weeks of SAP; Group B 8 weeks of USS +SAP(d) Second Phase: Group A 8 weeks of USS +SAP(d); Group B 8 weeks of USS + CLC(d) Third Phase: Group A 8 weeks of USS + CLC(d); Group B 8 weeks of USS +SAP (d) Fourth Phase: Group A 8 weeks of USS + SAP(d); Group B 8 weeks of SAP

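### SA1-3 claims that USS+SAP(d) beats SAP on fear of hypoglycemia and quality of life, but its assigned analysis is an undefined pre-post comparison that does not name SAP

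*Combined protocol and SAP*

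**What the plan says.** In Section 6.1 the hypothesis for Specific Aim 1 begins "Overnight CLC achieved by USS+SAP(d) will be superior to SAP alone in terms of", and its third item reads "Reduced fear of hypoglycemia and improved diabetes quality of life scores". The comparator is therefore SAP. Section 1.1 states the same aim.

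Under Primary Outcomes in Section 6.1, the only analysis given to that third item is "comparing the psychometric questionnaire scores pre-post treatment will address SA1-3". Pre, post and treatment are not defined, and SAP is not mentioned in the clause. The paragraph does open with the USS+SAP(d) versus SAP comparison, for the primary outcome (CGM time below 70 mg/dL without a rise in HbA1c).

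Section 6.1 also says that the overall analysis uses mixed models whose fixed factors follow the study design. It lists the questionnaires as a metric collected together with HbA1c, at five time points. Section 3.1 has HFS-II and DDS at screening. Sections 3.7 and 3.8 repeat the questionnaires after each phase.

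Section 3.7 sets the order of phases, ending with "Fourth Phase: Group A 8 weeks of USS + SAP(d); Group B 8 weeks of SAP". Section 1.5.2 notes that "some of the study participants will not have had experience with CGMs in the past".

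**The concern.** A claim that one modality is better than another needs scores on both. A pre-post change compares a modality with whatever came before it, and in this design that is seldom SAP.

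Two errors could follow. A favourable change could be read as a benefit of overnight closed loop over SAP when part of it comes from starting CGM, from training and staff contact, or simply from time in the study. Conversely, a real benefit could be diluted by the phases that start from USS+CLC(d), where subjects step down from 24-hour closed loop.

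**Working it through.** **The plan's own figure.** No number in the plan belongs to SA1-3. The nearest is the SA1 sample size in Section 6.2 (76 completers of 110 randomized). Use λ = N·m·f²/(1−ρ), with f = 0.2, ρ = 0.4, α = 0.01 and m = 4 repeated measures (m is not stated). Then 75 completers give 90% power and 76 give about 91%; 110 × 0.69 = 75.9. The figure is reproduced, and this point does not rest on it.

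**Step 1: which score precedes each USS+SAP(d) phase.** The sequences come from Section 3.7. The five time points are taken as screening plus the end of each of four phases.

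| Group, phase | Preceding score | SAP score? |
|---|---|---|
| A, phase 2 | end of SAP | yes |
| A, phase 4 | end of USS+CLC(d) | no |
| B, phase 1 | screening, usual care | no |
| B, phase 3 | end of USS+CLC(d) | no |

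The count is 1 of 4. If pre means screening throughout, it is 0 of 4.

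**Step 2: what the change estimates.** Write U, S and C for the mean score on USS+SAP(d), SAP and USS+CLC(d), B for usual care at screening, and π0 to π4 for drift with time in study. The four changes are:

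- A, phase 2: U − S + (π2 − π1)
- A, phase 4: U − C + (π4 − π3)
- B, phase 1: U − B + (π1 − π0)
- B, phase 3: U − C + (π3 − π2)

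The plan gives no weights. With equal weights (an assumption) the mean is

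U − [0.25 S + 0.50 C + 0.25 B] + 0.25 (π4 − π0).

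SAP carries a quarter of the comparator weight, and a quarter of the whole-study drift remains.

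**Step 3: illustrations, with assumed values and no drift.**

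- *False benefit.* Suppose CGM start and training improve fear by a lasting 0.2 to 0.4 SD and closed loop adds nothing. Group B phase 1 then shows 0.2 to 0.4 SD, and the equal-weight mean shows 0.25 × (0.2 to 0.4) = 0.05 to 0.10 SD. With screening as pre, all four cells show 0.2 to 0.4 SD. The CGM part applies only to subjects new to CGM, whose share is not given.
- *Dilution.* Suppose U improves on S by d, C equals U, and B equals S. The equal-weight mean is d − 0.50 d = 0.5 d, half the true benefit.

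**Step 4: what the design offers.** In phase 1, Group A is on SAP and Group B on USS+SAP(d). In phase 4 they are the other way round. Hence

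- A4 − A1 = (U − S) + (π4 − π1)
- B1 − B4 = (U − S) − (π4 − π1)

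Their average is U − S: common drift cancels, provided there is no carry-over and drift is the same in both groups. In phases 2 and 3 neither group is on SAP, so those USS+SAP(d) scores have no concurrent SAP control.

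**The case against.** The strongest reply is that the clause is ambiguous rather than wrong. It could mean change from screening to the end of phase 1, compared between groups. That would be a randomized comparison of USS+SAP(d) with SAP, with much of the training and time in study shared. The clause also closes a paragraph that opens with that comparison, and the general mixed-model sentence covers the listed aims and would bring modality into the model. This stands in part. A reader might infer that SA1-3 is not tested at all, or that the crossover is not used. The documents do not support either statement, because a modality contrast is available under the general sentence. But that sentence sets no contrast for the questionnaires, and the clause specific to SA1-3 assigns something else. The plan thus allows analyses that estimate different quantities.

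A reader might also infer from the 1-of-4 count that Group B has no useful adjacent scores. That is not so. Group B moves from USS+SAP(d) in phase 3 to SAP in phase 4, which is the same comparison with the sign reversed. The count concerns only what precedes USS+SAP(d).

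Some Group B subjects may already use CGM with their pump at entry, so their screening score may resemble SAP. It is still not a score after the 8-week SAP phase, and it will not be available for everyone.

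Finally, a reader might infer that no quality-of-life scale is used, since the Visit 1 list names none. The questionnaires are in Appendix A-11, which is not in the text reviewed, so this cannot be verified.

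**Conclusion.** The concern holds as a mismatch between claim and assigned analysis. SA1-3 names SAP as comparator; its own analysis clause does not, and leaves pre undefined. On either within-group reading, the pre score is a SAP score in at most 1 of 4 cells, and the change mixes in CGM start, training, time in study or step-down from USS+CLC(d).

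The count rests only on the phase order and the questionnaire timing. The 0.25/0.50/0.25 weights assume equal weighting, and the SD figures and the half-benefit case are illustrations, not estimates from the documents.

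This should be corrected before analysis, but its weight is moderate. SA1-3 is a supporting item, not the designated primary outcome of SA1, and the scores needed for the right comparison are already planned.

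**What to change.** Replace the SA1-3 clause in Section 6.1 with:

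> SA1-3 will be addressed by the within-subject contrast of end-of-phase HFS-II and DDS scores on USS+SAP(d) minus SAP, from the mixed model with modality, phase and sequence as fixed effects and the screening score as covariate. The main contrast uses phases 1 and 4, where one group is on SAP and the other on USS+SAP(d). The USS+SAP(d) scores from phases 2 and 3 are supportive.

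Report change from screening as descriptive only. As a side matter, name the instrument that carries the quality-of-life claim; if Appendix A-11 holds none, reword the claim to diabetes distress.

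The cost is wording alone: no new visit, instrument or subject. Two limits should be stated. First, staff contact is closer in the first closed-loop phase (Section 3.11) than during SAP (Section 3.9), and the new contrast does not remove that difference. Second, Section 6.2 does not say to which SA1 outcome f = 0.2 applies. If it is applied to this two-condition contrast (m = 2), λ = 76 × 2 × 0.04/0.6 = 10.1 and power at α = 0.01 is about 70%; 90% would need 115 completers. That is context for reading a null result on a supporting item, not a reason to change N.
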